PLANNED TRIAL PERIODS (for the whole study)	
The total duration of the study will be approximately 42 months, including approximately a 18-month enrolment period.
 
Planned start date (first patient on study): approximately first quarter 2015.
 
Planned enrolment period: approximately 18 months.
 
Planned end-of-study date (clinical cutoff): 24 months after randomization of the last patient.

SCHEDE OF ASSESSMENTS AND PROCEDURES

Assessments and procedures	Screening* (days before first drug infusion)	Treatment						End of treatment (EOT) ‡	Follow-up		
		Cycle 1		Cycle 2**		Further cycles**					
		D1	D8	D1	D8	D1	D8				
Written informed consents (general and for pharmacogenetic and PGx sub-study)	Before any study procedure	-	-	-	-	-	-	-	-		
Demographic data	-28 to 0	-	-	-	-	-	-	-	-		
Medical and cancer history/baseline conditions	-14 to 0 (+1 week)	-	-	-	-	-	-	-	-		
Assessment of disease-related signs and symptoms	-14 to 0 (+1 day)	-	-	-	-	-	-	-	-		
Complete physical examination, including weight, height and calculation of BSA (1)	-14 to 0 (+1 day)	-	-	•	-	•	-	-	-		
ECOG PS	-7 to 0 (+1 day)	-	-	•	-	•	-	•	-		
Vital signs (heart rate, blood pressure, temperature)	-7 to 0 (+1 day)	-	-	•	-	•	-	-	-		
Laboratory tests (2)	-7 to 0 (+3 days)	-	•	•	•	•	-	•	-		
Pregnancy test (if applicable) (3)	-7 to 0 (+3 days)	Repeat if applicable						-			
ECG (4)	-7 to 0 (+3 days)	Repeat if clinically indicated						-			
LVEF by ECHO or MUGA	-14 to 0 (+2 weeks)	Repeat if clinically indicated In patients treated with PLD (Arm B), to be repeated every four cycles (or more frequently, if clinically indicated). After exceeding a cumulative anthracycline dose of 450 mg/m ² , LVEF will be assessed before each PLD infusion						-			
Pharmacokinetics (PM01183 treatment arm only, in Cycle 1 and in a second cycle between Cycle 2 and Cycle 4)	-	• (5)	• (5)	• (6)	• (6)	• (6)	• (6)	-	-		
Pharmacogenetics (polymorphisms), in Cycle 1 only if written informed consent given	-	• (7)	-	-	-	-	-	-	-		
Pharmacogenomics (PGx), if written informed consent given	Available stored paraffin-embedded tumor tissue samples	-						-			
Radiological tumor assessment (contrast enhanced helical CT-scan or MRI, as clinically relevant)	-14 to 0 (+2 weeks)	Every eight weeks from randomization until evidence of PD						• (8)			
Tumor marker evaluation (CA-125)	-7 to 0 (+3 days)	Every eight weeks from randomization until evidence of PD (9)						• (9,10)			

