Patient-reported outcomes (EORTC QLQ-C30 and EORTC QLQ-OV28 questionnaires)	-7 to 0 (+1 day)	Every eight weeks from randomization				•	-				

Assessments and procedures	Screening* (days before first drug infusion)	Treatment						End of treatment (EOT) †	Follow-up		
		Cycle 1		Cycle 2**		Further cycles**					
		D1	D8	D1	D8	D1	D8				
Concomitant therapies	-14 to 0	Throughout the "on-treatment period"***						-			
Adverse events	- §	Throughout the "on-treatment period"***						• (11)			

Regardless of the treatment administered, the same schedule of assessments will apply.

* Screening procedures will have to be repeated in case that the first infusion of the study treatment is given out of the established windows. **Note: Randomization of patients should occur as close in time as possible to the administration of the first dose of study drug.**

**Further treatment cycles will be administered every three weeks (\pm 48 hours) for PM01183 (Arm A) and topotecan (Arm B), or every four weeks (\pm 48 hours) for PLD (Arm B) if the patient fulfills all re-treatment criteria.

***"On treatment period" = from first infusion of the study treatment (PM01183, PLD or topotecan) to EOT [30 days after the day of the last dose administration, unless the patient starts a new antitumor therapy or dies (whichever occurs first), in which case the date of administration of this new therapy or the date of death will be considered the date of end of treatment].

† At 30 \pm 7 days after the last treatment infusion, an EOT should be performed. The listed assessments will have to be done if no recent data are available (i.e. within last 10 days prior to the EOT visit) or if the last data available show a grade \geq 2 treatment-related alteration whenever the medical condition of the patient may allow these evaluations.

§ Only information on SAEs that occur after signature of informed consent form is required. Grading should be as per NCI-CTCAE v. 4.

Time windows for Cycle 2 and further: a 3-day window will be allowed for laboratory tests and ECG, a 1-week window for tumor assessments as per RECIST v.1.1, tumor marker evaluation and patient-reported outcomes, a 1-day window for clinical assessments (ECOG PS, vital signs, weight, BSA, etc.), a 7-day window for the assessments at EOT, and a 2-week window for the follow-up period.

1. Height to be measured at baseline only.

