3. OVERALL STUDY DESIGN

Multicenter, open-label, randomized, controlled phase III clinical trial to evaluate the activity and safety of PM01183 *versus* PLD or topotecan as control arm in patients with platinum-resistant ovarian cancer.

A single-agent PM01183 dose will be explored in the experimental arm (Arm A) *versus* PLD or topotecan in the control arm (Arm B).

Central randomization will be implemented in all patients that fulfill the inclusion criteria; patients will be assigned to each treatment arm at a 1:1 ratio. If the patient had not previously received PLD or topotecan, the assigned treatment in case that the patient is randomized to the control arm (Arm B) will be based on the reported Investigator's preference with regard to each one of these two drugs. However, if the number of patients randomized to either PLD or topotecan reaches 60% of the total number of patients expected in the control arm (i.e. 126 patients), then the treatment of choice in the control arm will be restricted to the less frequent control drug until the end of accrual. Once the 60% is achieved for one of the two control agents, then the patient will not be eligible for this trial if this agent is the only possible option (e.g., the patient has been previously treated with topotecan, then PLD is the only possible option in case the patient is randomized to the Arm B despite the fact that an accrual of 60% has been reached for PLD). Stratification will be performed according to Eastern Cooperative Oncology Group (ECOG) performance status (PS) (0 vs. ≥ 1), prior platinum-free interval (1-3 months vs. >3 months), and prior chemotherapy (1-2 vs. 3 lines).

Up to 420 patients will be included in the trial.

An Independent Data Monitoring Committee (IDMC) will oversee the conduct of the study. Operational details for the IDMC will be detailed in the corresponding charter.

An Independent Review Committee (IRC) will determine the best patient's response and assign the date of objective response or progression/censoring according to RECIST

v.1.1. Operational details for the IRC and the algorithm and its validation by an expert panel is described in detail in the IRC charter.

[figure not shown]

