5.4 PRE-TREATMENT ASSESSMENTS

During the pre-treatment period, following signature of the ICF, the Investigator will confirm the patient's eligibility for the study by conducting the assessments summarized in [Table 5](#).

Table 5. Screening period: pre-treatment assessments.

	ASSESSMENT	TIME
1. Written informed consent (general and pharmacogenetic and PGx sub-study)		Before any study procedures.
2. Medical and cancer history/ clinical examination	♦ Demographic data.	Within 28 days prior to first infusion.
	♦ Medical and cancer history/baseline condition: 
 ◦ Primary diagnosis. ◦ Prior treatments (with best response and TTP, when available). ◦ Documented date of relapse. ♦ Disease-related signs and symptoms. ♦ Complete physical examination, including weight, height and calculation of BSA. ♦ Concomitant therapies. 	Within 14 days prior to first infusion.*/**
	♦ Performance status (ECOG PS).	Within 7 days prior to first infusion.*
	♦ Vital signs: heart rate, blood pressure and body temperature.	
3. Laboratory tests	♦ Hematology: differential WBC counts (including neutrophil, lymphocyte and monocyte counts), platelet count and hemoglobin. ♦ Biochemistry: Liver function test (ALT, AST, AP, GGT, total bilirubin; direct bilirubin only if total bilirubin is abnormally high); total proteins, albumin, creatinine, CPK, glucose, calculated CrCL (as per Cockcroft and Gault's formula), and serum electrolytes (Na ⁺ , K ⁺ , Cl ⁻).	Within 7 days prior to first infusion.***
4. Pregnancy test (if women of childbearing potential)	Assessment of β-hCG (urine or serum).	Within 7 days prior to first infusion, if applicable.***
5. ECG	Cardiac rhythm will be identified in ECG intervals of at least 30 seconds of duration, PR interval, QT interval (raw), heart rate and QRS complex.	Within 7 days prior to first infusion.***
6. LVEF	ECHO or MUGA.	Within 14 days prior to first infusion.****
7. PGx	Available stored paraffin-embedded tumor tissue samples; only in those patients that give their written informed consent for the PGx sub-study.	-

	ASSESSMENT	TIME
8. Radiological tumor assessment	Contrast enhanced helical CT-scan or MRI, as clinically relevant.	Within 14 days prior to first infusion.***
9. Tumor marker evaluation	CA-125.	Within 7 days prior to first infusion.***
10. Patient-reported outcomes	EORTC QLQ-C30 and EORTC QLQ-OV28 questionnaires.	Within 7 days prior to first infusion.*

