11. Adverse events	Only information on SAEs that occurred after signature of the informed consent is required before treatment start. Grading should be as per the NCI-CTCAE v.4.	-

Regardless of the treatment administered, the same schedule of assessments will apply.

*A 1-day window is allowed for assessment of disease-related signs and symptoms, complete physical examination, ECOG PS, vital signs, and patient-reported outcomes at screening.

**A +1-week window is allowed for medical and cancer history/baseline conditions at screening.

***A +3-day window is allowed for laboratory tests, CA-125 assessment, pregnancy tests and ECG at screening.

****A +2-week window is allowed for LVEF and tumor assessments as per RECIST v.1.1.

ALT, alanine aminotransferase; AP, alkaline phosphatase; AST, aspartate aminotransferase; β -hCG, beta subunit of human chorionic gonadotropin; BSA, body surface area; CPK, creatine phosphokinase; CrCL, creatinine clearance; CT, computed tomography; ECG, electrocardiogram; ECHO, echocardiography; ECOG, Eastern Cooperative Oncology Group; EORTC, European Organization for Research and Treatment of Cancer; GGT, gamma glutamyltransferase; LVEF, left ventricular ejection fraction; MRI, magnetic resonance imaging; MUGA, multiple-gated acquisition scan; NCI-CTCAE, National Cancer Institute Common Terminology Criteria for Adverse Events; PGx, pharmacogenomics; PS, performance status; RECIST, Response Evaluation Criteria In Solid Tumors, SAE, serious adverse event; TTP, time to progression; WBC, white blood cells.

Screening procedures will have to be repeated in case that the first infusion of the study treatment is given out of the established windows.

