5.6 PATIENT RANDOMIZATION

Central randomization will be implemented in all patients that fulfill the inclusion criteria. Randomization of patients should occur as close in time as possible to the administration of the first dose of study drug. Patients will be assigned to each treatment arm at a 1:1 ratio. If the patient had not previously received PLD or topotecan, the assigned treatment in case that the patient is randomized to the control arm (Arm B) will be based on the reported Investigator's preference with regard to each one of these two drugs. However, if the number of patients randomized to either PLD or topotecan reaches 60% of the total number of patients expected in the control arm (i.e. 126 patients), then the treatment of choice in the control arm will be restricted to the less frequent control drug until the end of accrual. Stratification will be performed according to ECOG PS (0 vs. ≥ 1), prior PFI (1-3 months vs. >3 months) and prior chemotherapy (1-2 vs. 3 lines).

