8.1 Baseline and Demographic Data

Baseline data such as demographics, cancer history, number of organs involved and sites of disease, prior therapy, laboratory values at baseline, prior relevant history, signs and symptoms, electrocardiogram, and concomitant medication [Anatomical Therapeutic Chemical – World Health Organization (ATC-WHO) coded] will be described following standard tables (detailed in Appendix I) for all randomized patients.

For pre-treatment characteristics with multiple measurements per patient before the start of treatment (e.g. laboratory assessments, vital signs), the baseline measurement will be considered the last value prior to or on the first day of treatment for tabulation and analysis. However all the baseline assessments will be listed (see section 13).

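### The plan times the baseline quality-of-life questionnaires to first infusion, not randomization, so in this open-label trial a patient may answer them after she knows her arm

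*SAP*

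**What the plan says.** Protocol section 3 describes a "Multicenter, open-label, randomized, controlled phase III clinical trial". In the schedule of assessments the screening column counts days before first drug infusion, and the PRO row reads -7 to 0 (+1 day). Table 5 in Protocol 5.4 gives the same timing for the "EORTC QLQ-C30 and EORTC QLQ-OV28 questionnaires": "Within 7 days prior to first infusion", with a 1-day window. Section 5.4 adds: "Screening procedures will have to be repeated in case that the first infusion of the study treatment is given out of the established windows". The questionnaires are not exempted.

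On the gap between allocation and treatment, Protocol 5.6 says: "Randomization of patients should occur as close in time as possible to the administration of the first dose of study drug". It sets no maximum number of days.

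SAP 8.1 covers pre-treatment characteristics measured more than once, with laboratory values and vital signs as examples. For these, "the baseline measurement will be considered the last value prior to or on the first day of treatment for tabulation and analysis". SAP 8.4 and 12.8 give no separate baseline rule for PRO. Baseline PRO scores are tabulated among the baseline characteristics (Table 11.1.6.1). They feed the change-from-baseline t-tests (Table 12.8.2), the proportions improving by at least 10% (Table 12.8.3) and the longitudinal model with time counted from baseline (Table 12.8.4). Baseline global QoL is a candidate covariate in the multivariate efficacy models of SAP 6.2.

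**The concern.** In an open-label trial the patient can learn her arm as soon as it is assigned. Self-reported scores can move with relief or disappointment at that news. A baseline answered afterwards may then differ between arms for a reason unrelated to treatment, and randomization no longer protects the comparison of baselines. Any such difference carries into the change scores. Global QoL, used as a covariate, would also no longer be strictly pre-randomization.

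The rules allow this in two ways. The questionnaire can be given inside its window but after randomization, for example on Cycle 1 Day 1. Or a valid pre-randomization answer can fall out of its window because dosing slips; the repeat then follows allocation, and the last-value rule selects the repeat.

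**Working it through.** The plan states no figure on this point, so there is none to reproduce. Two things can be checked: when the rules permit a late answer, and how much a late answer could matter.

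**Timing.** Let g be the number of days from randomization to first infusion. The documents do not give g, so it is an assumption. The window of -7 to 0 holds 8 calendar days, and min(g, 8) of them fall after the day of randomization.

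| g (days) | In-window days after randomization |
|---|---|
| 0 | 0 of 8 |
| 1 | 1 of 8 (12%) |
| 3 | 3 of 8 (38%) |
| 5 | 5 of 8 (62%) |
| 7 | 7 of 8 (88%) |
| 8 or more | 8 of 8 (100%) |

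If the extra day widens the early side (-8 to 0, 9 days), g = 3 gives 3 of 9 (33%), g = 7 gives 7 of 9 (78%), and g of 9 or more gives all 9.

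**Repeat rule.** An answer given k days before randomization leaves the 7-day window when k + g > 7. With k = 5 and g = 3, 5 + 3 = 8 > 7, so even a short gap can require a repeat after allocation. Reading the window as 8 days moves the limit to k + g > 8.

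**Size.** Assumptions, none from the documents: SD of change 20 to 25 points, and 150 to 180 patients per arm with data. Let d be the between-arm difference in reaction, in points, among patients who answer late, and p the share answering late in each arm. The reaction is taken to be gone at follow-up.

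- SE = SD × √(2/n). SD 20 with n = 180 gives 2.11; SD 25 with n = 150 gives 2.89.
- Average baseline shift between arms = p × d.
- Two-sided false-positive rate = P(|Z + p·d/SE| > 1.96).

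| p | d = 3 points | d = 5 points |
|---|---|---|
| 25% | shift 0.75; 5.8% to 6.5% | shift 1.25; 7.2% to 9.1% |
| 100% | shift 3; 18% to 30% | shift 5; 41% to 66% |

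In each cell the lower rate goes with SE 2.89 and the higher with SE 2.11. At p = 10% the rates for both values of d lie between 5.1% and 5.6%.

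**Direction.** If control patients are disappointed and score low at baseline, they appear to improve later; relief in Arm A does the reverse. The excess false positives would then almost all favour control.

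**The case against.** The strongest reply is that the intended workflow puts screening before randomization. Protocol 5.4 says the Table 5 assessments are used to confirm eligibility, only eligible patients are randomized, and Protocol 7.4.2 describes the screening phase as ending at randomization. Dosing is also meant to follow randomization closely, and with a gap of zero no in-window day falls after the randomization day. This limits the exposure but does not remove it. Section 7.4.2 concerns SAE reporting. The questionnaire is not an eligibility criterion, so checking eligibility does not force it before allocation. Its window and repeat rule both refer to the infusion.

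Second, SAP 8.1 does not name PRO. That is correct, and applying it to PRO is an inference from its general wording and from where the baseline PRO table sits. If it does not apply, the SAP has no rule for choosing between two baseline questionnaires.

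Third, follow-up answers are unblinded too. If the reaction to allocation persists, a post-allocation baseline would partly cancel it, whereas a pre-randomization baseline would leave it in the change score. This stands. The fix makes the baselines comparable between arms; it does not remove open-label reporting bias at follow-up.

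Fourth, misordering can partly be detected: all baseline assessments are to be listed, and the listings carry the questionnaire date and the date and time of randomization.

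A reader might infer three stronger things that the documents do not support. One is that PRO error rates are inflated to 18-66%; that needs nearly every patient to answer after allocation, and no frequency is given. Another is that the bias favours the experimental drug; the direction described works against it. The third is that baseline CA-125 and albumin are compromised as covariates; knowing the arm before any dose does not plausibly change a laboratory value.

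**Conclusion.** The point holds as a gap in the rules. The protocol permits a baseline PRO score to be self-reported after the patient knows her arm, and the general wording of SAP 8.1 would prefer that score to an earlier one. Under the stated assumptions the effect on error rates is small if a minority answer late: about 6% for a 3-point reaction and 7-9% for a 5-point reaction at 25% late. It is large only if nearly all do. These figures also assume that the reaction fades by follow-up.

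The damage is confined to the secondary PRO comparisons and to baseline global QoL, one of many candidates in supportive multivariate models. The primary stratified log-rank test of PFS by IRC is not affected. The change is worth making because it is cheap and a missed pre-allocation answer cannot be recovered later.

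**What to change.** - **Protocol Table 5 and the schedule of assessments:** require both questionnaires after consent and before randomization, or at the latest before the arm is disclosed. Either exempt them from the repeat rule or state that a later repeat does not replace the baseline.
- **SAP 8.1 and 8.4:** define baseline for PRO scores, including global QoL as a covariate, as the last value on or before randomization. List later pre-dose repeats. Keep the last value up to first treatment for laboratory and other safety shifts.

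This also gives a defined PRO baseline to patients randomized but never treated (Listing 10.1.5), who have no first day of treatment, and puts baseline on the same clock as the later questionnaires, which run from randomization.

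The cost is about one sentence in each document and no new assessment. The downside is that for some patients the PRO baseline will lie a few days further from first dose.

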8.2 Protocol Deviations

Analysis of protocol deviations following the ‘Protocol Deviation and Non-Compliance Management Plan’ will be done as described in Appendix I.

8.3 Treatment Administration

Total cumulative dose, time on treatment, dose intensity and relative dose intensity, administration delay, and dose reductions/omissions will be described following standard tables (detailed in Appendix I) and the reported cycle information on the case report form (CRF) pages will be used for the analyses.

Total cumulative dose by drug, expressed in mg, is the sum of all the product doses from the first cycle until the last cycle, including the dose received in the last cycle.

Time on treatment, expressed in weeks, is defined as last infusion date minus first infusion date plus 30 days, except if the patient dies or starts a new antitumor therapy within 30 days from the last infusion date, in which case the time on treatment will be the date of death or the date of the start of a new antitumor therapy minus the date of the first infusion.

Intended dose intensity is the planned dose per cycle divided by the planned number of weeks by cycle.

Absolute dose intensity is the actual cumulative dose divided by the number of weeks of treatment. As a convention, for this calculation, the duration of the last cycle will be the predefined cycle length (i.e., 21 days or 28 days in case of PLD). Relative dose intensity (%) is the ratio of absolute dose intensity divided by the intended dose intensity.

The items « Infusion delayed: yes/no» and « Dose reduced: yes/no» present on the drug

administration CRF page will be used to calculate delays and dose reductions, respectively. For cycles considered as delayed by the Investigator, the length of the delay will be calculated as:

Duration of cycle delay: Date of the current drug administration – Date of the previous drug administration – the predefined cycle length (i.e., 21 days if PM01183/topotecan or 28 days if PLD).

8.4 Patient-reported Outcomes (PRO)

To measure the quality of life of patients, EORTC QLQ-C30 and EORTC QLQ-OV28 questionnaires will be analyzed every eight weeks from randomization and while on treatment.

PRO will be analyzed by means of longitudinal modelling and T-test comparisons to determine if efficacy and side effects are accompanied by measurable changes. The analysis will be performed on summary scores of EORTC QLQ-C30 and EORTC QLQ-OV28 questionnaires, as well as on subscales and individual symptoms.

